### 8.2.2. Analysis of Primary Endpoint

An intention to treat analysis will be conducted of the primary outcomes for the study. Assuming that a descriptive comparison of the intervention to control group does not demonstrate statistically significant differences in terms of demographics, vaccine drivers/barriers, or vaccine knowledge, we will report on the relative rate of influenza vaccination for the intervention group compared to the control group. We will also conduct logistic regression modeling of influenza vaccination as follows:

$$logit(Y) = \beta_0 + \beta_1 M + \sum_{j} \beta_j \alpha_j + \varepsilon$$

Where:

logit(Y) = ln(Y/1-Y) for the binary variable designation of influenza vaccination status M = the binary designation for Intervention (messaging) vs Control (no messaging)  $\alpha_j =$  the baseline covariates measured in the study (e.g. demographics, vaccine drivers/barriers or knowledge)

 $\varepsilon$  = the error term of the regression.

For the logistic regression model the p-values associated with each of the  $\beta$  parameter estimates will be reported.

Version 1 17 of 22

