4 SAMPLE SIZE

We determined sample size for a two-arm interventional statistical superiority study design with vaccination rates as the primary outcome of interest (Zhong 2009). Studies on the impact of messaging and reminders to improve influenza vaccination rates show a range of effect sizes from 2.5 - 3.5% (Nehme et al., 2019, Hurley et al., 2018). As noted earlier, CDC reported vaccination rates are 47.9% for adults between the ages of 18 - 65.

Given these a-priori assumptions, we assumed different baseline vaccination rates of 35%, 50% and 60%, and then computed the sample size needed to detect an increase in vaccination rate of 2%, 3% and 4% respectively. Sample size for the difference in proportion is determined by (Zhong, 2009):

$$N = \frac{1}{2} \left(\frac{z_{\alpha/2} + z_{\beta}}{arcsin\sqrt{p} - arcsin\sqrt{p_0}} \right)^2$$

Where:

 $Z_{\alpha/2}$ and Z_{β} refer to the z critical values for a type I and II error of 0.05 and 0.2 respectively, p_0 and p are the baseline proportion and the new hypothesized proportion respectively, and N is the total sample size, assuming a 1:1 ratio of intervention to control

Baseline vaccination rate	Hypothesize d vaccination rate	Hypothesize d effect size	Hypothesize d Cohen's h	Sample size
35.0%	37.0%	2.0%	4.2%	18080
50.0%	52.0%	2.0%	4.0%	19610
60.0%	62.0%	2.0%	4.1%	18668
35.0%	38.0%	3.0%	6.2%	8080
50.0%	53.0%	3.0%	6.0%	8710
60.0%	63.0%	3.0%	6.2%	8256
35.0%	39.0%	4.0%	8.3%	4570
50.0%	54.0%	4.0%	8.0%	4894
60.0%	64.0%	4.0%	8.2%	4618

In the above table, for each baseline rate and hypothesized rate increase (and associated Cohen's h), we show the estimated total sample size needed for each assumption of baseline vaccination rate and effect size. We note that within each hypothesized effect size, changing assumptions about baseline vaccination rates do not substantially alter the sample size.

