Based on this, we believe that a 3% effect size is a reasonable assumption and that a sample size of approximately 8,000 participants will be needed to detect this difference with a type I error rate of 0.05 and a presumed power of 0.80. A participation drop-off of 67% has been observed for digital interventions for increasing influenza vaccination in people with diabetes (i.e., Samson et al., 2020). A recent internal survey of individuals with cardiovascular disease demonstrated a survey completion rate of approximately 7%, indicating that this population may have lower than expected engagement. Based on these calculations, we plan to recruit approximately 49,000 participants, anticipating that on average, engagement may be approximately 16%. A targeted enrollment list of approximately 49,000 individuals with 16% survey completion would reach the estimated analysis population of 8,000 participants needed.

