7 DATA COLLECTION

- Data from self-reported survey:
 - Demographics
 - Medical history
 - Health behaviors
 - Healthcare utilization
 - o Influenza vaccination status, experience, and complications
 - o COVID-19 experiences
 - Vaccine attitudes and barriers
 - o Influenza risks and healthcare provider role
 - Experience and perceptions of intervention materials (CVD-I only)
- Data from engagement with interventions (CVD-I only)
 - o For example, clicks, dismissals, or completions of interventions
- Data from Achievement Profile
 - Activity data generated by wearables (e.g., heart rate, sleep, step data), from 12 months before participation and 12 months after participation (if available)

	Source	Retrospective 12 months before to 12 months after	Demographics Survey	Baseline	Month 3	Month 6
Self-reported data						
Demographics	Survey		Х			
Medical history	Survey		Х			
Health behavior history & influenza vaccination	Survey		Х			
Healthcare utilization	Survey			Х	Х	Х
Influenza vaccination status	Survey			X	Х	Х
Influenza experience & complications	Survey			Х	Х	Х
COVID-19 experiences & perceptions	Survey			Х	Х	Х
Vaccine drivers & barriers	Survey			Х	Х	Х
Influenza risks & healthcare provider role	Survey			Х	Х	Х
Experience and perceptions of intervention materials	Survey					X (CVD-I only)

Engagement with interventions	Achievement website/app and Survey Monkey		[] (CVD-I only)	
Activity tracker data				
Steps	[e.g. Fitbit, Garmin]	Х	[]	
Sleep	[e.g. Fitbit, Beddit]	Х	[]	
Heart rate	[e.g. Fitbit, Apple]	Х	[]	

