8 STATISTICAL METHODS

8.1 General Statistical Approaches

For the study variables, we will perform distributional analysis. When describing the study population, we will use min, max, mean, and standard deviations for continuous variables (i.e. age, BMI) and frequency counts for categorical variables (i.e. gender, ethnicity). For both continuous and categorical variables, we will report on the number of participants evaluated for that variable, as well as the number of people with non-missing values. For the study variables, we will also look at individual-level rates of missing data. Missing data or unknown responses will be described separately and not be counted in the summary descriptions of the variables. We will report on the percent of missing data for each of the included data sources (surveys, activity data) and evaluate whether any missingness is associated with baseline participant-level characteristics in the case of missing survey data or with the outcome in the case of activity tracker data.

Statistical testing comparing variables will be performed at the 5% significance level using two-sided tests or two-sided 95% confidence intervals (CI), unless otherwise specified. Comparison of means will use Student's t-test for normal distributions, or a Mann-Whitney U test for non-normal distributions. Comparisons of frequencies will use chi-square tests. Regression modeling approaches are described below. We will report on the size of the beta-parameter estimate and the associated significance level (p-value) for each predictor variable.

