8.5 Primary objective analysis

An intention to treat analysis will be conducted of the primary outcomes for the study. Assuming that a descriptive comparison of the intervention to the control group does not demonstrate statistically significant differences in terms of demographics, vaccine drivers/barriers, or vaccine knowledge, we will report on the relative rate of influenza vaccination for the intervention group compared to the control group. This is given simply by:

RR = rate of influenza vaccination among intervention group rate of influenza vaccination among control group

We will also conduct logistic regression modeling of influenza vaccination as follows:

$$logit(Y) = \beta_0 + \beta_1 M + \sum_i \beta_i \alpha_i + \varepsilon$$

Where:

logit(Y) = ln(Y/1-Y) for the binary variable designation of influenza vaccination status M = the binary designation for Intervention (messaging) vs Control (no messaging) $\alpha_j = the$ baseline covariates measured in the study (e.g. demographics, vaccine drivers/barriers or knowledge) $\epsilon = the$ error term of the regression.

Vaccine drivers and barriers are described above in Section 8.1: Derived Variables

For the logistic regression model the p-values, odds ratio and associated 95% CI associated with each of the β parameter estimates will be reported.

Kaplan-Meier curves will be constructed for time-to-influenza vaccination, using the participant estimated dates of influenza vaccination from the 3 and 6 month surveys.

- 8.6 Secondary objective analysis
- 8.6.1 To examine predictors of vaccination status, including cardiovascular condition type, vaccine drivers/barriers, and vaccine knowledge, across and between CVD-I and CVD-C.

To examine predictors of vaccination status, including cardiovascular condition type, vaccine drivers/barriers, and vaccine knowledge, across CVD-I and CVD-C we will construct the model:

$$logit(Y) = \beta_0 + \sum_i \beta_i P_i + \sum_i \beta_i \alpha_i + \varepsilon$$

Where:

logit(Y) = ln(Y/1-Y) for the binary variable designation of influenza vaccination status P_i = the predictor of interest i (e.g. cardiovascular condition, vaccine drivers/barriers, vaccine knowledge) α_j = the baseline demographics ϵ = the error term of the regression.

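### The headline relative rate is unadjusted and the primary logistic model does not commit to using influenza vaccination history, although a survey row for it is scheduled: forgone precision of uncertain size

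*SAP*

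**What the plan says.** - **Headline estimate.** SAP 8.5: if a descriptive comparison shows no significant imbalance, "we will report on the relative rate of influenza vaccination for the intervention group compared to the control group". The formula that follows is one arm's rate over the other's, with no covariates.
- **Primary model.** SAP 8.5 adds a logistic model with arm and "baseline covariates measured in the study (e.g. demographics, vaccine drivers/barriers or knowledge". Protocol 8.2.2 uses the same description. P-values, odds ratios and confidence intervals in SAP 8.5 are attached to this model.
- **What the named groups contain.** SAP 7.1 lists drivers and barriers as primary care visits, cardiology visits, hospitalisation, being offered the vaccine and being told of high risk. Knowledge is the set of information sources used. Neither includes past vaccination. The baseline comparison in SAP 8.4 uses the same three groups.
- **What is collected.** The table in SAP 7 has a row "Health behavior history & influenza vaccination" in the demographics survey column. It is separate from current vaccination status, which is asked at baseline, month 3 and month 6. The protocol's table in section 7 matches.
- **When and from whom.** SAP 5 makes every survey optional and keeps the demographics survey open throughout the study. The primary analysis population, P1 in SAP 8.2, is everyone who answers the 3-month or 6-month survey; the demographics survey is not required.

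**The concern.** Vaccination in past seasons is the same behaviour as the primary outcome, so one would expect it to predict that outcome at least as well as the groups the plan names. The trial looks for a 3-point difference. If a strongly prognostic variable is collected but not used, the interval is wider and the chance of missing the planned effect is higher than it need be, and recovering that loss would require no additional participants. There is a second, smaller cost. With an open covariate list, whether history enters the primary model can be decided after the data are seen, so the primary adjusted estimate is not fully prespecified.

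**Working it through.** **1. The plan's own sample size.** SAP 4 gives z values that "refer to the z critical values for a type I and II error of 0.05 and 0.2 respectively", and SAP 8.1 states "Statistical testing comparing variables will be performed at the 5% significance level using two-sided tests". The arcsine formula, with z = 1.960 and 0.842, gives n per arm; doubling gives the total. For a 3-point increase:

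| Control rate | n per arm | Total | SAP table |
|---|---|---|---|
| 35% | 4041.0 | 8082 | 8080 |
| 50% | 4355.3 | 8710.5 | 8710 |
| 60% | 4128.3 | 8256.6 | 8256 |

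The table reproduces, and it assumes no covariate adjustment.

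**2. Unadjusted power at the target.** Inputs: about 8,000 respondents, 1:1, so 4,000 per arm (SAP 4); control rate 47.9%, the surveillance figure quoted in SAP 1 and 4; a 3-point effect ("we believe that a 3% effect size is a reasonable assumption"), so 50.9%.

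- Variance sum: 0.479 × 0.521 + 0.509 × 0.491 = 0.4995
- Standard error: √(0.4995 / 4000) = 0.01117
- Power: Φ(0.03 / 0.01117 − 1.96) = Φ(0.725) = 76.6%

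The same calculation at control rates of 35%, 50% and 60% gives 79.6%, 76.6% and 78.8%. The shortfall below 80% comes from rounding 8,080-8,710 down to 8,000, not from the choice of covariates.

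**3. Adjustment for history.** Let rho be the correlation between past and current vaccination, and c the share of P1 with the item. Neither is in the documents; both are assumptions. The variance is multiplied by v = 1 − c·rho², and power = Φ(0.03 / (0.01117·√v) − 1.96). Worked case, rho = 0.5 and c = 1: v = 0.75, standard error 0.00968, power Φ(3.100 − 1.96) = 87.3%.

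| rho | Power, c = 50% | Power, c = 100% | Gain over 76.6% (points) |
|---|---|---|---|
| 0.2 | 77.4% | 78.2% | 0.8 to 1.7 |
| 0.3 | 78.4% | 80.4% | 1.9 to 3.8 |
| 0.5 | 81.9% | 87.3% | 5.3 to 10.7 |
| 0.7 | 87.1% | 96.4% | 10.5 to 19.8 |

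At c = 30% the gain is 1.1 points at rho = 0.3 and 3.1 at rho = 0.5.

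**4. Simulation check.** A crude test was compared with a Cochran-Mantel-Haenszel test stratified on history, with half of participants previously vaccinated, full coverage and 20,000 trials per scenario. Uptake of 65% vs 35% by history (rho = 0.3) gave a gain of 3.8-4.0 points; 70% vs 30% (rho = 0.4) gave 6.7-6.9; 75% vs 25% (rho = 0.5) gave 10.5. These agree with the formula. A smaller simulation (3,000 trials) of the logistic model with a not-reported category, at rho = 0.5, gave gains of 9.6 points at full coverage (77.3% to 86.9%) and 4.2 at half (79.2% to 83.4%).

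**5. What was not computed.** The comparator throughout is an unadjusted analysis. The gain over the planned model, with its demographics, care contacts and vaccine-offer items, was not estimated. Completion of the demographics survey that differs by arm was not modelled.

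**The case against.** The strongest reply is that nothing planned fails. The sample size assumes no adjustment and reproduces. The primary model may already include history, since its list is introduced by e.g. and the item sits in the demographics survey. That stands as far as it goes: for the logistic model one can say only that the plan does not commit. For the relative rate, the absence of adjustment is explicit.

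It is also fair that the row label names no season. The questionnaire is not in the documents, and the word history may belong only to health behaviour. The remedy must therefore be conditional on what the item asks. The survey is optional and may be answered after messages have been sent, so an answer is not automatically a baseline value. Missing answers are not a reason to reject the covariate, however: the SAP 7 table places demographics in this same optional survey, so the covariates already named face the same gap.

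A reader might infer three stronger things that the documents do not support:

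- **That history is left out of the primary model.** The open list does not say so.
- **That the omission leaves the trial underpowered by a known amount.** Quoting 5-11 points alone fixes rho at 0.5 and coverage at 50-100%, neither of which is documented.
- **That adjustment would correct differential survey response between arms.** P1 consists of respondents only, and an optional, partly missing item that may be answered after randomisation cannot be assumed to remove that selection.

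**Conclusion.** The point holds as forgone precision in the primary analysis, and acting on it is worthwhile because the row is already scheduled for collection. Its size is uncertain: about 1 to 4 power points for a weak association (rho 0.2-0.3), 5 to 11 for a moderate one (0.5) and 10 to 20 for a strong one (0.7), in each case with 50-100% coverage and against an unadjusted analysis of 8,000 respondents. At 30% coverage it is about 1 to 3 points for rho 0.3-0.5. Overlap with the planned covariates would reduce the increment over the planned model. The conclusion depends on the item covering seasons before the study, which has to be confirmed from the questionnaire.

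**What to change.** In SAP 8.5:

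1. Confirm from the questionnaire that the item covers seasons before the study. If it does, name past-season influenza vaccination as a prespecified covariate in the primary logistic model, coded yes / no / not reported so that all of P1 is kept. Do not use answers about the current season, which the messages could have affected.
2. Report vaccination rates by arm standardised from that model, and their ratio, beside the crude relative rate. The adjusted odds ratio is conditional, so the standardised rates should carry the interpretation.
3. Show the not-reported share and the time of completion by arm.
4. Add two sensitivity analyses: one that omits the covariate, and one restricted to people who reported history.

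The cost is SAP wording and a little programming, with no new data and no more participants. The drawback is that the item is self-reported, optional and may be completed after randomisation. The SAP should therefore present the adjustment as a gain in precision and make no claim that it corrects selection from differential survey response.

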The digital intervention messages were developed using a 3-part approach: 1) a quantitative assessment of more than 800 patient perspectives for people with cardiovascular disorders, assessing their behaviors, thoughts, and beliefs surrounding vaccination; 2) semi-structured interviews with approximately 25 patients who had cardiovascular diseases to gather their perspectives and feedback on proposed intervention messages; and 3) an expert panel of cardiologists, behavioral scientists, and vaccine policy experts for expert input on content and accuracy of scientific information provided. This approach to intervention development was consistent with the Patient Centered Outcomes Research Institute (PCORI) recommendation for developing interventions that increase participant recruitment and retention, improve patient outcomes, and increase research validity and relevance to the real world (Frank, Basch, & Selby, 2014). The intervention messages provide informational content on the influenza vaccine (sourced from the Centers for Disease Control and Prevention and the American Heart Association), specific information about influenza and cardiovascular disorders, and behavioral prompts (e.g., reminders) surrounding influenza vaccination behaviors.

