7.1 Derived Data

Cardiovascular condition type will be one of the following for the purposes of the secondary analysis objectives:

- People with self-reported arrhythmia only (not including atrial fibrillation)
- People with self-reported atrial fibrillation only
- People with self-reported heart attack, cardiac arrest or coronary artery disease only
- People with self-reported congestive heart failure only
- People with self reported stroke only
- People with two or more of the above conditions
- People with other cardiovascular conditions

Vaccine drivers and barriers of interest include:

- Number of visits to a primary care provider in the 3 months prior (categorized as None, 1-2, 3 or more)
- Number of visits to a cardiology specialist in the 3 months prior (categorized as None, 1-2, 3 or more)
- Hospitalization in the 3 months prior (categorized as none, once, 2 or more)
- Offered influenza vaccination by a healthcare provider (categorized as Yes, No, Unsure)
- Healthcare provider informed individual they were in a 'high risk group' (categorized as Yes, No, Unsure)

Vaccine knowledge factors are based on responses to the survey question "What sources of information do you use to learn about the flu vaccine?", with possible responses:

- Healthcare Professionals
- Family member or peers
- Social media including blog posts
- Mobile applications
- Conventional news media (e.g. television, newspapers)

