8.2 Analysis Population (s)

The analysis populations will consist of:

- P1: This population will consist of all individuals who respond to the 3-month or 6-month survey. It will
 be used for the primary objective analysis and for the first part of the secondary objective (examine
 predictors of vaccination status across the CVD-I and CVD-C arms). This population will also be used
 for the second exploratory objective, which is to describe self-reported complications from influenza
 during the study period.
- P2: This population will consist of all individuals who are in the CVD-I arm and have responded to the 3-month or 6-month survey. It will be used for the second part of the secondary objective, which is to describe the engagement with different intervention messages and its relationship to influenza vaccination status.
- P3a: This population will consist of individuals who responded to the baseline, 3-month or 6-month survey. It will be used to examine the first part of the exploratory objectives - specifically the selfreported impact of COVID-19 on influenza vaccination and behavior.
- P3b: This population will consist of all individuals who complete either the 3-month or the 6-month survey, who have wearable activity data and who consent in the final (6-month) survey to have the activity data analyzed for this study. This population will be used for the 3rd exploratory objective, specifically to explore the differences in wearable data (i.e., sleep, steps, heart rate) between individuals who experience influenza and those who do not, as well as differences in wearable data between cardiovascular conditions.

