Cardiovascular condition type is described above in Section 8.1: Derived Data. Vaccine drivers and barriers are described above in Section 8.1: Derived Variables. The beta-parameter estimates, p-values, adjusted odds ratio and 95% CI will be reported. SHapley Additive exPlanations (SHAP) values will be used to assess the individual contributions of each predictor variable [Lundberg, 2017].

To describe the predictors of vaccination status and how it varies between CVD-I and CVD-C, we will use the model:

$$logit(Y) = \beta_0 + \beta_1 P + \beta_2 C + \sum_i \beta_i P_i * C + \sum_i \beta_i \alpha_i + \varepsilon$$

Where the variable *C* is a binary (1,0) designation for CVD-I and CVD-C respectively, and the beta-estimate for interaction term will be reported with the corresponding p-value, adjusted odds ratio and 95% CI. As with above, the SHAP values will be used to evaluate the individual contributions of each predictor variable.

People who report getting the influenza vaccination are asked a series of behavioral and attitudinal questions around where, how and when the vaccination was received. Those survey responses will be summarized for the study population. Similarly, people who did not obtain an influenza vaccine are asked a set of questions around attitudes and willingness to vaccinate, and those will also be summarized. Changes in response to questions on vaccine drivers and barriers will be examined between the baseline survey and the final survey.

8.6.2 To describe engagement with interventions, including clicking, opening, or completing the intervention messages

To examine differences in vaccination rates between individuals in the CVD-I group and its relationship to engagement with intervention messages, we will model:

$$logit(Y) = \beta_0 + \beta_1 M + \sum_i \beta_i \alpha_i + \varepsilon$$

Where:

logit(Y) = In(Y/1-Y) for the binary variable designation of influenza vaccination status M = the number of engaged messages (ordinal variable 0, 1, 2, 3, 4, 5, 6) α_i = the baseline covariates measured in the study (e.g. demographics, CVD type)

- 8.7 Exploratory objective analysis
- 8.7.1 To describe the self-reported impact of the COVID-19 pandemic on influenza vaccination behavior Descriptive summaries of the participant responses to the monthly survey questions on COVID-19 will be

provided.

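### The pooled predictor model in SAP 8.6.1 leaves out the randomised arm and names no survey wave for its predictors, so a predictor that differs by arm would absorb part of the intervention effect

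*SAP*

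**What the plan says.** The across-arm model in SAP 8.6.1, introduced with "vaccine drivers/barriers, and vaccine knowledge, across CVD-I and CVD-C we will construct the model", is a logistic regression with an intercept, a set of predictors and a set of covariates. The predictors are defined as "the predictor of interest i (e.g. cardiovascular condition, vaccine drivers/barriers, vaccine knowledge". The covariates are "the baseline demographics". Neither definition includes the arm. The across-arm model in Protocol 8.2.3 has no arm term either.

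Two neighbouring SAP models do have one. The primary model in 8.5 contains the messaging indicator M. The second model in 8.6.1, which asks how predictors vary between arms, contains C, which "is a binary (1,0) designation for CVD-I and CVD-C respectively", together with predictor-by-C interactions.

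The population for the across-arm model is P1, defined in SAP 8.2: "This population will consist of all individuals who respond to the 3-month or 6-month survey". A baseline response is not required. The schedule in SAP 7 collects drivers and barriers at baseline, month 3 and month 6. SAP 7.1 lists provider visits, hospitalisation, being offered vaccination and being told of high-risk status as drivers or barriers. It lists information sources, including "Mobile applications", as knowledge factors. Section 8.6.1 gives no survey wave for any of them.

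**The concern.** The trial pools two arms that it hopes will differ in vaccination, then models vaccination without the variable expected to cause the difference. That is harmless for any predictor distributed alike in the two arms. For one that is not, its coefficient mixes its own association with vaccination and its role as a marker of arm.

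A difference by arm could arise in two ways:

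- **Messaging.** Only CVD-I receives the messages. SAP section 1 says of them: "The intervention messages provide informational content on the influenza vaccine". They also carry behavioural prompts. Answers recorded after messaging could therefore differ by arm.
- **Response.** Randomisation balances the roughly 49,000 people on the target list, not the 16% or so expected to complete surveys. Only CVD-I gets messages and points for completing them (Protocol 6.5), which could affect who answers.

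At stake are the odds ratios, p-values and SHAP contributions reported for this secondary objective. The primary comparison is untouched.

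**Working it through.** **Inputs.** Control vaccination rate 50%, effect 3 points, about 8,000 analysed at 1:1, so 4,000 per arm (SAP 4). Two-sided 5% tests (SAP 8.1). The share of each arm with the predictor, q0 in CVD-C and q1 in CVD-I, is an assumption, because the documents give none.

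**The plan's own figure.** The plan gives no operating characteristics for this model, so the check is on the sample-size row that supplies the inputs. For 50% vs 53% the arcsine difference is 0.030018. Then (1.960 + 0.842)/0.030018 = 93.33, its square is about 8,710, and half of that is 4,355. This is the per-arm number. Doubled, it gives the tabulated total of 8,710, so the row reproduces.

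**Induced association.** Let the predictor have no effect within either arm.

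- Share from CVD-I among those with the predictor: f1 = q1/(q0 + q1)
- Share from CVD-I among those without it: f0 = (1 − q1)/(2 − q0 − q1)
- Spurious difference in vaccination: 0.03 × (f1 − f0)

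For 10% vs 30%:

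- f1 = 0.30/0.40 = 0.75 and f0 = 0.70/1.60 = 0.4375.
- Difference = 0.03 × 0.3125 = 0.0094, giving vaccination rates of 0.5225 and 0.5131.
- Odds ratio = (0.5225/0.4775)/(0.5131/0.4869) = 1.038.
- Group sizes are 4,000 × 0.40 = 1,600 and 4,000 × 1.60 = 6,400. The pooled rate is 0.515.
- SE = √[0.515 × 0.485 × (1/1,600 + 1/6,400)] = 0.01397, so z = 0.0094/0.01397 = 0.67.
- Rejection probability = Φ(0.67 − 1.96) + Φ(−0.67 − 1.96) ≈ 0.099 + 0.004 = 0.103.

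**All settings.** The last two columns come from 2,000 simulated trials per setting, with the predictor as the only covariate besides arm.

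| Prevalence, CVD-C vs CVD-I | Spurious difference (points) | Spurious OR | Rejection, normal approximation | Simulated, no arm term | Simulated, with arm term |
|---|---|---|---|---|---|
| 10% vs 10% | 0 | 1.000 | 5.0% | 4.9% | 5.0% |
| 10% vs 20% | 0.59 | 1.024 | 6.6% | 7.0% | 4.6% |
| 10% vs 30% | 0.94 | 1.038 | 10.3% | 10.7% | 5.6% |
| 10% vs 50% | 1.43 | 1.059 | 21.6% | 21.0% | 4.5% |

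The simulation standard error at 5% is √(0.05 × 0.95/2,000) = 0.5 points, so the last column is consistent with the nominal level.

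**Sensitivity.** For 10% vs 30%, a 2-point effect gives 7.3% and a 4-point effect 14.5%. With a 3-point effect, control rates of 35% and 60% give 10.8% and 10.5%.

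**The case against.** The best reply is that the predictors are baseline values. SAP 8.4 and 8.5 treat drivers, barriers and knowledge as baseline variables, and randomisation precedes every study activity. On that reading they are balanced in expectation, and the first row of the table applies. This is a fair reading, but 8.6.1 does not state it. There the word baseline is attached only to the demographics, and SAP 8.6.1 also plans to examine changes in drivers and barriers from baseline to the final survey. Baseline values could also be unbalanced within P1 if response differs by arm. That P1 needs no baseline survey shows only that later values could be used, not that they will be.

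A second reply is that the between-arm model already supplies an arm-adjusted check. SAP 8.1 calls for a coefficient and p-value for every predictor in a regression, so it would be wrong to say that only the interaction is reported from that model. That stands. However, with C coded 1 and 0 the predictor's main effect there is the association in the control arm, not the pooled association that the across-arm analysis is meant to give.

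Third, the SAP states no null hypothesis for this analysis, and in a purely predictive sense a marker of arm does predict vaccination. That also stands. The case for the arm term is that an objective about condition type, drivers and knowledge is more usefully read with arm held fixed.

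**Conclusion.** The omission is real and the mechanism is confirmed, but the consequence is conditional and small. It needs a predictor whose distribution differs by arm, through messaging or differential response. For assumed shifts from 10% to 20%, 30% or 50%, a nominal 5% test rejects about 7%, 10% or 21% of the time, with odds ratios of about 1.02 to 1.06. With balance there is no inflation.

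A reader might infer that the messages will raise the "Mobile applications" answer in CVD-I, and that this item will then be declared a predictor merely for marking that arm. The documents do not support that. Nothing in them says messaging changes this or any other listed predictor, and people in both arms already use the Achievement platform and receive offers through it. Condition type is a diagnosis that messaging would not plausibly alter.

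The analysis is secondary and the primary result does not depend on it. The severity is minor, and the change is worth making because it is nearly free.

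**What to change.** In SAP 8.6.1, add the arm indicator to the across-arm model: logit(Y) = β0 + βC·C + Σ βi·Pi + Σ βj·αj, with C as already defined for the next model. Take the reported odds ratios, p-values and SHAP values for the predictors from this model.

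In the same place, take the predictors from the baseline survey where available, or name the wave that supplies each one. If baseline values are used, say how P1 members without a baseline survey are handled. Their number cannot be worked out from the documents.

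Arm is known for everyone, so the term loses no data and costs one degree of freedom in about 8,000. It removes arm-marking only. If values recorded after messaging are used, mediation and reverse causation remain (for instance, being offered the vaccine at the visit where it is given), and the report should say so.
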